# 8.3.1.1 Urticaria Patient Daily Diary (UPDD)

UPDD includes Urticaria Activity Score (UAS) which assesses twice daily severity of itch and number of hives, use of rescue medication, sleep and activity interference, angioedema occurrence, its management and records the calls to a healthcare professional (HCP). The components are presented in the Table 8-2 and the relevant weekly scores are described below.

Table 8-2 UPDD

Diary component	When assessed
Urticaria Activity Score (UAS)	Morning and evening
Itch severity	
Number of hives	
Sleep interference	Morning
Daily activity interference	Evening
Rescue medication use	Evening
Angioedema:	Evening
Whether patient had an episode	
If patient had an episode, how did they manage it	
Contact health care provider	Evening

### 8.3.1.1.1 Weekly Hives Severity Score (HSS7)

The hives (wheals) severity score, defined by number of hives, will be recorded by the participant twice daily in their eDiary, on a scale of 0 (none) to 3 (> 12 hives/12 hours; Table 8-3). A weekly score (HSS7) is derived by adding up the average daily scores of the 7 days preceding the visit. The possible range of the weekly score is therefore 0 - 21.

Table 8-3 Hives Severity Score

Score	Hives (Wheals) (every 12 hours)
0	None
1	1-6 hives/12 hours
2	7-12 hives/12 hours
3	>12 hives/12 hours

### 8.3.1.1.2 Weekly Itch Severity Score (ISS7)

The severity of the itch will be recorded by the participant twice daily in their eDiary, on a scale of 0 (none) to 3 (severe) (Table 8-4). A weekly score (ISS7) is derived by adding up the average daily scores of the 7 days preceding the visit. The possible range of the weekly score is therefore 0 - 21.

Table 8-4 It	ch Severity Score
--------------	-------------------

Described (Mark) (assess 40 house)	
Score	Pruritus (Itch) (every 12 hours)
0	None
1	Mild (minimal awareness, easily tolerated)
2	Moderate (definite awareness, bothersome but tolerable)
3	Severe (difficult to tolerate)

# 8.3.1.1.3 Weekly Urticaria Activity Score (UAS7)

The UAS7 is the sum of the HSS7 score and the ISS7 score. The possible range of the weekly UAS7 score is 0-42 (highest activity).

### 8.3.1.1.7 Angioedema occurrence

Angioedema occurrence is recorded once daily in the evening in the eDiary by the participant. Reporting the occurrence of angioedema will be used as opening question for the assessment of the AAS (see Section 8.3.1.2). Actions and/or treatments related to those angioedema occurrences will be also recorded in the eDiary as follows (multiple answers possible):

- Did nothing
- Took some prescription or non-prescription medication
- Called my doctor, nurse or nurse practitioner
- Went to see my doctor, nurse or nurse practitioner
- Went to the emergency room at the hospital
- Was hospitalized.

### 8.3.1.1.8 Number of calls to doctor or nurse

The number of calls to doctor, nurse or nurse practitioner because of the participant's skin condition will be recorded once daily in the eDiary by the participant.

### 8.3.1.2 Angioedema Activity Score (AAS)

AAS is recorded once daily in the evening in the eDiary by the participant. This validated tool assesses occurrence of episodes of angioedema. As an opening question, the occurrence of angioedema in the UPDD (see Section 8.3.1.1.7) will be used. If participants answer this opening question in the UPDD with "no", AAS score for this day is 0. If "yes" is the answer to the opening question in the UPDD, the participant will continue to answer questions about the duration, severity and impact on daily functioning and appearance of the angioedema (see Appendix 5). A score between 0 and 3 is assigned to every answer field. The AAS score in this study will be reported as weekly AAS (AAS7). Minimum and maximum possible AAS7 scores are 0–105. A higher score means higher severity.

# 8.3.2 Other Patient Reported Outcomes (PRO) assessments

# 8.3.2.1 Dermatology Life Quality Index (DLQI)

The DLQI is a 10-item (grouped in 6 domains) dermatology-specific quality of life (QoL) measure (Finlay and Khan 1994). The DLQI was validated for patients aged 16 and above. Participants rate their dermatology symptoms as well as the impact of their skin condition on various aspects of their lives thinking about the previous 7 days.

An overall score is calculated and ranges from 0 to 30 (higher score meaning worse disease-related QoL). Domain scores are calculated for: Symptoms and Feelings (0-6), Daily Activities (0-6), Leisure (0-6), Work and School (0-3), Personal Relationships (0-6), Treatment (0-3).

The overall DLQI score range was split into score bands (Hongbo et al 2005) and validated in terms of their meaning/relevance to patients as follows:

[figure not shown]
Table 8-7 DLQI score bands and impact on patient's life

DLQI band	Significance of score
0-1	No effect on patient's life
2-5	Small effect on patient's life
6-10	Moderate effect on patient's life
11-20	Very large effect on patient's life
21-30	Extremely large effect on patient's life

Amended Protocol Version No. 01 (Clean)

A DLQI score of > 10 is relevant for a very large impact on patients' life and justification for a biologic prescription for example in psoriasis (Finlay 2005). The DLQI questionnaires are completed at visits detailed in Table 8-1 in the eDiary. The DLQI should be completed prior to any other assessment and prior to administration of investigational medication.

[figure not shown]

### 8.3.3 Appropriateness of efficacy assessments

UAS7: The UAS7 score is a unified, simple, well-established and validated tool, recommended by the current urticaria guidelines for the assessment of disease activity and treatment response in real-world clinical practice as well as in clinical trials with urticaria patients (Młynek et al 2008, Hawro et al 2018, Zuberbier et al 2018). It is based on the assessment of the two key urticaria signs and symptoms, wheals and pruritus, which are documented by the patient, making this score especially valuable. The use of the UAS7 facilitates comparison of study results across different trials, since it is used in other major Phase 3 trials in the CSU indication as well (e.g., with ligelizumab).

AAS7: The AAS7 score is a unified, simple and validated tool, recommended by the current urticaria guidelines for the assessment of disease activity and treatment response in patients with angioedema (Weller et al 2013, Zuberbier et al 2018). The use of the AAS7 facilitates comparison of study results across different trials, since it is used in other major Phase 3 trials in the CSU indication as well (e.g., with ligelizumab).

### 8.3.4 Other assessments: evidence of urticaria

The investigator must confirm the presence of urticaria (i.e., the presence of hives) in each participant before starting the study treatment by direct physical examination. In the absence of active disease at the screening and/or baseline visit, the following will be acceptable: (a) a clearly identifiable photograph of the participant that is no older than 3 months showing the presence of urticaria, (b) the investigator must have seen the participant with active CSU in the past 3 months, or (c) the presence of hives/wheals must have been documented in the medical

record of the participant by a physician trained in the management of urticaria in the past 3 months.

# 8.4 Safety

Safety assessments are specified below with the assessment schedule detailing when each assessment is to be performed.

For details on AE collection and reporting, refer to AE section.

As per Section 4.6, during a Public Health emergency as declared by Local or Regional authorities, i.e., pandemic, epidemic or natural disaster, that limits or prevents on-site study visits, regular phone or virtual calls can occur (every 4 weeks or more frequently if needed) for safety monitoring and discussion of the participant's health status until it is safe for the participant to visit the site again.

Table 8-8 Physical assessments

Assessment	Specification
Physical examination	A complete physical examination (performed at Screening) will include the examination of general appearance, skin, neck (including thyroid), eyes, ears, nose, throat, lungs, heart, abdomen, back, lymph nodes, extremities, vascular, neurological and body temperature measurement (per local practice). If indicated based on medical history and/or symptoms, rectal, external genitalia, breast, and pelvic exams will be performed.  A short physical exam (performed at all visits except Screening) will include the examination of general appearance, assessment of the skin for signs of urticaria and other skin lesions, body temperature measurement (per local practice) and vital signs (blood pressure (BP) [systolic blood pressure (SBP) and diastolic blood (DBP)] and pulse).  Information for all physical examinations must be included in the source documentation at the study site. Clinically relevant findings that are present prior to signing informed consent must be recorded on the appropriate CRF that captures medical history. Significant findings made after signing informed consent which meet the definition of an Adverse Event must be recorded as an adverse event.
Vital signs	Vital signs include BP and pulse measurements. After the participant has been sitting for five minutes, with back supported and both feet placed on the floor, systolic and diastolic blood pressure will be measured three times using an automated validated device, e.g., OMRON, with an appropriately sized cuff. The repeat sitting measurements will be made at 1 - 2 minute intervals and the mean of the three measurements will be used. In case the cuff sizes available are not large enough for the participant's arm circumference, a sphygmomanometer with an appropriately sized cuff may be used. Clinically notable vital signs are defined in Section 16.1.
Height and weight	Height in centimeters (cm) and body weight (to the nearest 0.1 kilogram (kg) in indoor clothing, but without shoes) will be measured as specified in Table 8-1.

# 8.4.1 Laboratory evaluations

A central laboratory will be used for analysis of all specimens detailed in this section (Table 8-9) unless noted otherwise. Details on the collections, shipment of samples and reporting of results by the central laboratory are provided to investigators in the laboratory manual.

If participants cannot visit the site for protocol specified safety lab assessments (per Section 4.6), an alternative lab (local) collection may be used.

Clinically notable laboratory findings are defined in Section 16.1.

Clinically significant abnormalities must be recorded on the relevant section of the eCRF capturing medical history/current medical conditions/AEs.

Table 8-9 Laboratory assessments

Table 6-3	Laboratory assessments
Test Category	Test Name
Hematology	Hematocrit, Hemoglobin, [in the case of clinically significant anemia the following parameters will be assessed: Ery. Mean Corpuscular Hemoglobin (MCH), Ery. Mean Corpuscular Hemoglobin Concentration (MCHC), Ery. Mean Corpuscular Volume (MCV)], Platelets, Erythrocytes, Leukocytes, and Differential (Basophils, Eosinophils, Lymphocytes, Monocytes, Neutrophils, Bands)
Chemistry	Albumin, Alkaline phosphatase (ALP), Alanine Aminotransferase (ALT), Aspartate Aminotransferase (AST), Gamma-glutamyl-transferase (GGT), Lactate dehydrogenase (LDH), Calcium, Magnesium, Phosphate, Chloride, Sodium, Potassium, Creatinine, Creatine Kinase (CK), Direct Bilirubin, Indirect Bilirubin (in case of clinically significant elevation), Total Bilirubin, Total Cholesterol, Low Density Lipoprotein (LDL) Cholesterol, High Density Lipoprotein (HDL) Cholesterol, Total Protein, Triglycerides, Urea Nitrogen or Urea, Uric Acid, Amylase, Lipase C-reactive protein (CRP), estimated Glomerular Filtration Rate (eGFR): in all patients at screening, baseline, Weeks 12, 24 and 52 and when deemed necessary by the investigator at any other visits than those listed. Fasting glucose assessed at baseline, Weeks 2, 12 and 52.
Urinalysis	Done on site: Macroscopic Panel (Dipstick) (Color, Bilirubin, Occult Blood, Macroscopic Blood, Glucose, Ketones, Leukocytes esterase, Nitrite, pH, Protein, Specific Gravity, Urobilinogen)
Coagulation	Prothrombin time (PT), International normalized ratio (INR), Activated partial thromboplastin time (APTT)
Hepatitis screening	Hepatitis B screening: Antibodies against Hepatitis B virus core antigen (HBcAb or anti-HBc); antibodies against Hepatitis B virus surface antigen (HBsAb or anti-HBs); Hepatitis B virus surface antigen (HBsAg).
	Hepatitis B virus-Deoxyribonucleic acid (HBV-DNA, only in participants who are positive for HBcAb or anti-HBc). The study site may refer to local guidelines for hepatitis B monitoring.
	Hepatitis C screening: Hepatitis C virus antibodies (anti-HCVAb) and Hepatitis C-Ribonucleic acid (HCV-RNA, only in participants who are positive for anti-HCVAb)
Hepatitis B re- activation	Only in participants who are positive for HBcAb (anti-HBc positive) and negative for HBsAb and HBV-DNA at screening: HBsAg, HBV-DNA.
monitoring	The study site may refer to local guidelines for hepatitis B re-activation monitoring.
HIV testing	HIV test performed at screening, only when required by local regulations.
Additional tests	Follicle-stimulating hormone (FSH) (for female participants with unclear fertility status)
Pregnancy Test	Serum / Urine pregnancy test for WoCBP (refer to Section 8.4.3)

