- 14. Evidence of clinically significant cardiovascular (such as but not limited to myocardial infarction, unstable ischemic heart disease, NYHA Class III/IV left ventricular failure, arrhythmia and uncontrolled hypertension within 12 months prior to Visit 1), neurological, psychiatric, pulmonary, renal, hepatic, endocrine, metabolic, hematological disorders, gastrointestinal disease or immunodeficiency that, in the investigator's opinion, would compromise the safety of the participant, interfere with the interpretation of the study results or otherwise preclude participation or protocol adherence of the participant
- 15. Uncontrolled disease states, such as asthma, or inflammatory bowel disease, where flares are commonly treated with oral or parenteral corticosteroids
- 16. Hematology parameters at screening:
  - Hemoglobin: < 10 g/dL
  - Platelets: < 100 000/mm^3
  - Leucocytes: <3 000/mm^3
  - Neutrophils: < 1 500/mm^3
- 17. Significant bleeding risk or coagulation disorders
- 18a. History of gastrointestinal bleeding, e.g., in association with use of nonsteroidal antiinflammatory drugs (NSAIDs), that was clinically relevant (e.g., for which intervention was indicated or requiring hospitalization or blood transfusion)
- 19a. Requirement for anti-platelet medication, except for acetylsalicylic acid up to 100 mg/d or clopidogrel up to 75 mg/d. The use of dual anti-platelet therapy (e.g., acetylsalicylic acid + clopidogrel) is prohibited.
- 20. Requirement for anticoagulant medication (e.g., warfarin or Novel Oral Anti-Coagulants (NOAC))
- 21. History or current hepatic disease including but not limited to acute or chronic hepatitis, cirrhosis or hepatic failure or Aspartate Aminotransferase (AST)/ Alanine Aminotransferase (ALT) levels of more than 1.5 x upper limit of normal (ULN) or International Normalized Ratio (INR) of more than 1.5 at screening
- 22. History of renal disease, creatinine level above 1.5x ULN, or estimated Glomerular Filtration Rate (eGFR) <45 ml/min (using the Cockcroft-Gault equation) at screening
- 23. Evidence of an ongoing Hepatitis C infection (e.g., defined by the detection of hepatitis C-ribonucleic acid (HCV-RNA) at screening) and/or an ongoing Hepatitis B infection (defined by the detection of Hepatitis B virus surface antigen (HBsAg) and/or hepatitis B virus (HBV)-DNA at screening; participants who are positive for anti-hepatitis B core

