- (HBc) antibodies but who are negative for antibodies against HBsAg and HBV-DNA can be included into the study if they agree to monitoring for HBsAg and HBV-DNA reactivation).
- 24. Known or suspected ongoing, chronic or recurrent infectious disease including but not limited to opportunistic infections (e.g., tuberculosis, atypical mycobacterioses, listeriosis or aspergillosis) and/or known positivity for Human Immunodeficiency Virus (HIV) infection.

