**Novartis** 

Investigational or other study treatment dose adjustments are not permitted.

Study treatment interruptions are permitted in order to manage the following events:

- Management of bleeding events: in case of planned surgery with clinical significant bleeding risk, interruption of study treatment 7 days before the surgery is required; after recovery, participant may re-start study treatment after 7 days.
- Management of participants in case of Hepatitis B re-activation (new appearance of detectable HBV-DNA or positive HBsAg): participants should start antiviral treatment according to local clinical practice and interrupt study treatment until HBV-DNA and HBsAg reach an undetectable level, and then re-start study treatment.

Study treatment interruption for other than the above reasons is only permitted if, in the opinion of the investigator, a participant is deemed to be at a significant safety risk unless administration of investigational treatment is temporarily interrupted. In such cases study treatment should be interrupted only during the time that this risk is present and ongoing. Study treatment can be restarted at the next scheduled visit after resolution of the safety risk.

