### 8 Visit schedule and assessments

The Assessment Schedule (Table 8-1) lists all of the assessments and when they are performed. All data obtained from these assessments must be supported in the participant's source documentation

Participants should be seen for all visits/assessments as outlined in the assessment schedule (Table 8-1) or as close to the designated day/time as possible. Missed or rescheduled visits should not lead to automatic discontinuation.

For participants who discontinue from study treatment refer to Section 9.1.1.

Participants who discontinue from the study or withdraw their consent/oppose the use of their data/biological samples should be scheduled for a final evaluation visit, if they agree, as soon as possible, at which time all of the assessments listed for the final visit will be performed. At this final visit, all dispensed investigational product should be reconciled, and the adverse event and concomitant medications not previously reported must be recorded on the CRF.

The "X" in the table denotes the assessments to be recorded in the clinical database or received electronically from a vendor. The "S" in the table denotes the assessments that are only in the participant's source documentation and do not need to be recorded in the clinical database.

As per Section 4.6, during a Public Health emergency as declared by Local or Regional authorities i.e., pandemic, epidemic or natural disaster that limits or prevents on-site study visits, alternative methods of providing continuing care may be implemented by the investigator as the situation dictates. If allowed by local Health Authority and depending on operational capabilities, phone calls, virtual contacts (e.g., tele consult) or visits by site staff/ home nursing staff to the participant's home, can replace on-site study visits, for the duration of the disruption until it is safe for the participant to visit the site again.

The preferred sequence of assessments during study visits is PRO completion, ECG collection, followed by vital signs, and blood sampling.

Table 8-1 Assessment Schedule

Tubic 0-1	SAPACACA SANA	-		0.6500										2	P
Period	Screening		3 £	70 8	7	70	75	Tre	atmen	t	2 1	20	2	Follow-up	Unsched uled

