Davs	-28 to -1	1	15	29	57	85	113	141	169	225	281	-	365	394	-

any other physician assessment.

 Hepatitis B re-activation monitoring only for participants who were HBsAg negative and HBcAb (anti-HBc) positive with a negative HBV DNA test at Screening.

<sup>15 HIV test will be performed only when required an allowed by local regulations.

The last response should be performed at Week 56 as study completion. However, if participants enroll the extension study, this should be done at the timing of Week 52.

<sup>18 Dispensation for background medication covers prescription, dispensation and/or instruction of the participant on dosing and use of background medication and protocol requirements, considering different procedures for the provision of background medication at investigational sites. At Week 56/Safety FU/Study completion visit only compliance to be checked.

<sup>19 Only for participants who have completed Week 52 visit, not applicable at Study discontinuation visit

<sup>20 Trial Feedback Questionnaire is not considered study data and will be received electronically outside the clinical database

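### Two safety rules, who is monitored for hepatitis B re-activation and what follows platelets below 75 000/mm3, are each worded inconsistently in the current protocol

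*Protocol*

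**What the plan says.** **Hepatitis B.** Three places in the protocol bear on who is monitored.

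- Table 8-9 (Section 8.4.1), re-activation row: "Only in participants who are positive for HBcAb (anti-HBc positive) and negative for HBsAb and HBV-DNA at screening". Those tested have HBsAg and HBV-DNA measured.
- Table 8-1 (Section 8), footnote 14: "Hepatitis B re-activation monitoring only for participants who were HBsAg negative and HBcAb (anti-HBc) positive with a negative HBV DNA test at Screening".
- Exclusion criterion 23 (Section 5.2): ongoing hepatitis B infection is "defined by the detection of Hepatitis B virus surface antigen (HBsAg) and/or hepatitis B virus (HBV)-DNA at screening". The proviso for people with core antibody reads "antibodies but who are negative for antibodies against HBsAg and HBV-DNA can be included into the study". It attaches one condition to their inclusion: "if they agree to monitoring for HBsAg and HBV-DNA reactivation".

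The abbreviation list and the screening row of Table 8-9 treat HBsAb (antibody) and HBsAg (antigen) as separate tests. On re-activation, meaning new HBV-DNA or a positive HBsAg, Section 6.6 calls for antiviral treatment and tells the site to "interrupt study treatment until HBV-DNA and HBsAg reach an undetectable level, and then re-start study treatment".

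**Platelets.** Section 9.1.1 lists a count below 75 000/mm3 as its own bullet among the circumstances in which study treatment must be discontinued. Section 16.1 (Appendix 1) gives the same threshold alongside hemoglobin, leukocytes and neutrophils. It requires a re-test within 5 days and, if the abnormality is confirmed, says that discontinuation is to be considered.

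**The concern.** Each pair of instructions lets two sites act differently while each follows a stated rule.

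For hepatitis B, someone with past infection and surface antibody falls inside footnote 14 and outside Table 8-9. The Section 6.6 action depends on finding HBV-DNA or HBsAg, so a participant who is not tested cannot trigger it. Criterion 23 adds doubt about whether that person may enrol at all: the infection definition does not exclude them, but the proviso does not cover them either.

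For platelets, a confirmed low count is a compulsory stop in one section and a matter for consideration in another. Section 4.5 names bleeding among the potential risks of remibrutinib, so this stopping rule should have one meaning.

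**Working it through.** There is no planned figure to reproduce. The check compares the current texts and counts visits.

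**Hepatitis B, step 1: profiles.** Take people who are HBcAb-positive, HBsAg-negative and HBV-DNA-negative.

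| HBsAb | Excluded by infection definition | Covered by criterion 23 proviso | Monitored under footnote 14 | Monitored under Table 8-9 |
|---|---|---|---|---|
| Negative | No | Yes | Yes | Yes |
| Positive | No | No | Yes | Not required |

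The rules differ only in the second row.

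**Step 2: two readings of criterion 23.**

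- Reading A, the infection definition decides: the HBsAb-positive person can enrol, and the two monitoring rules disagree.
- Reading B, the proviso is a condition on every HBcAb-positive person: the HBsAb-positive person cannot enrol. Both rules then select the same participants, and 0 are discordant.

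**Step 3: size under reading A.** The re-activation row of Table 8-1 marks Weeks 4, 8, 12, 16, 20, 24, 32, 40 and 52, which is 9 tests for a completer. Week 56 adds one, 9 + 1 = 10, for those who do not enter the extension (Section 4.1). Table 8-9 requires 0 for the same person.

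**Step 4: which rule prevails?** Section 8 says "The Assessment Schedule (Table 8-1) lists all of the assessments and when they are performed", which favors footnote 14. Nothing states that Table 8-1 overrides Table 8-9. The sentence in Table 8-9 about local guidelines is permissive.

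**Platelets: side by side.**

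| Result below 75 000/mm3 | Section 9.1.1 | Section 16.1 |
|---|---|---|
| Single value, not yet re-tested | Discontinuation required; confirmation not mentioned | Re-test within 5 days |
| Confirmed value | Discontinuation required | Discontinuation to be considered |

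The first row can be reconciled. The platelet bullet sits under emergent AEs, and Section 10.1.1 makes a laboratory value an AE only under stated criteria, so re-testing first is a fair reading. The second row is the real conflict: a site that confirms the value and continues dosing has met Section 16.1 and breached Section 9.1.1. Within Section 9.1.1, the bullet for other laboratory abnormalities is left to investigator judgment and the renal and liver bullets refer to their appendices. The platelet bullet has neither feature.

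**The case against.** On platelets, Section 9.1.1 is specific and mandatory, while Section 16.1 is one general sentence over four parameters. A site that re-tests and then stops satisfies both. Section 9.1.1 also requires discontinuation wherever continued participation might pose a safety risk. A reader might infer that Section 16.1 licenses dosing after a confirmed low count; it does not expressly say so. This stands and makes the conflict narrow, but a site using the appendix alone would still find no mandatory stop.

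On hepatitis B, a reader might infer that HBsAb-positive participants will go unmonitored. The documents do not establish that. It requires that such people enrol, which criterion 23 leaves open, and that sites follow Table 8-9 rather than footnote 14. Operational detail is in a laboratory manual not available here. Exclusion 21, which removes anyone with a history of hepatitis, narrows the group further, though not necessarily to zero. General consent and the requirement to adhere to the protocol also weaken any argument that monitoring lacks the participant's agreement.

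It can also be said that two of the three texts use antibody wording, and that the amendment log describes the Table 8-9 hepatitis rows as aligned with central laboratory procedures, so moving to HBsAg might reverse the sponsor's intent. That is a fair reason to ask for confirmation. Against it, Table 8-9 orders HBV-DNA at screening for every HBcAb-positive person whatever the HBsAb result, which has little purpose if the HBsAb-positive can never enrol.

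**Conclusion.** Both inconsistencies are in the current amended protocol, and the SAP settles neither. They warrant a moderate correction to the safety text.

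- Hepatitis B: 9 scheduled tests (10 with Week 56) against none required, per affected completer, if HBcAb-positive, HBsAb-positive people enrol. If they cannot, only the eligibility wording is at issue.
- Platelets: a mandatory stop against a discretionary one, for a confirmed value only.

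The number affected is not given and may be zero for both. For platelets, entry requires at least 100 000/mm3, and cytopenias in the final Phase 2b analysis were all mild. Liver chemistry and hematology at every visit, the liver triggers and the DMC are partial backstops. The sample size and the descriptive analyses are unaffected.

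A reader might go further and infer, from the Section 6.6 sentence on restarting at a scheduled visit, that a low platelet count could cost a participant weeks of treatment. The documents do not support attaching that to this point. Neither platelet rule prescribes a hold. Outside the named events, a Section 6.6 interruption depends on the investigator's opinion that "a participant is deemed to be at a significant safety risk unless administration of investigational treatment is temporarily interrupted". The restart sentence is permissive, and Table 8-1 provides unscheduled visits with hematology.

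**What to change.** **Hepatitis B.** Keep footnote 14. In the Table 8-9 re-activation row, replace HBsAb with HBsAg. In the criterion 23 proviso, replace the reference to antibodies against HBsAg with HBsAg itself. Both then match footnote 14 and the exclusion definition. The sponsor should confirm that HBsAb-positive participants are meant to enrol with monitoring.

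Cost: up to 9 or 10 additional HBsAg/HBV-DNA tests per such participant where a site now follows Table 8-9, at visits that already draw blood. Enrolment may widen slightly if sites now apply the stricter reading.

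**Platelets.** In Section 16.1, take platelets out of the sentence on considering discontinuation, leaving hemoglobin, leukocytes and neutrophils there. State that a confirmed value below 75 000/mm3 requires discontinuation under Section 9.1.1. In Section 9.1.1, refer to the 5-day re-test.

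Cost: investigators lose discretion to continue after a confirmed value.

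Both changes need a protocol clarification and a notice to sites.
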